#### **Risks of Phlebotomy**

To minimize the risk of pain, bruising, lightheadedness, and on rare occasions, infection or fainting from a blood draw, we will used trained phlebotomists.

## **Physical discomforts:**

The drawing of blood may cause pain, bruising, lightheadedness, and on rare occasions, infection. Subjects may briefly feel the prick of the needle when it is inserted. Subjects may feel dizzy or faint when blood is drawn. Trained phlebotomists will be used to minimize these risks.

ECGs may cause discomfort and/or irritation of the skin (redness and itching) from the adhesive electrodes. Hair on your chest may need to be removed in order to obtain the best electrical contact between the adhesive electrodes and subjects' skin. Trained staff will be used to minimize these risks.

## **Risk to a developing fetus**

The administration of pitolisant in pregnant women has not established a known risk for major birth defects, miscarriage or adverse maternal or fetal outcomes. In animal reproductive studies, however, there is a known maternal and embryofetal toxicity in rats and rabbits.

To protect against the risk of potential developmental toxicity to a fetus, women will be excluded from study entry if they have a positive urine pregnancy test or if they are of childbearing age and are either not using appropriate methods of contraception or not practicing abstinence. Pitolisant may reduce the efficacy of oral contraceptives. If the subject's primary method of contraception is oral contraceptive, they will be required to use an approved back-up form of contraception beginning at first dose of pitolisant/placebo and continuing through 21 days following last dose. Urine pregnancy testing will also be completed at each study visit as a protection to the developing fetus. Subjects with positive pregnancy test results will be discontinued form participation.

### **Risks of alcohol self-administration**

#### Risk to recovery efforts

Treatment-seeking drinkers will be excluded from this study to minimize the risk that drinking in the laboratory could worsen outcomes for a subject trying to reduce or abstain from alcohol. All subjects will undergo a medical screening and we will exclude subjects who have diagnosed medical or mental condition for which alcohol exposure in this study would be contraindicated. All subjects will receive the NIAAA self-help guide *Rethinking Drinking* at the end of study participation.

#### Risk of overconsumption

To minimize the risk of subjects reaching a level of intoxication that is uncomfortable to them, we will remind subjects that they may discontinue study participation at any time. Subjects will be asked to drink to a target BAL (0.03 g/dl) that is customary for them given the minimum drinking criteria. The alcohol self-administration paradigm that we have chosen does not include any coercion, inducements, or pressure to consume more alcohol than subjects feel comfortable consuming. There are no experimental manipulations that would increase drinking (e.g., heavy drinking confederate, anxiety manipulation). In fact, in this study design there are inducements for subjects to not drink beyond the initial priming dose. Subjects will receive monetary incentives for each drink that they do not consume. Access to medical backup services will be maintained throughout each alcohol challenge session. Subjects will be monitored during the course of the study, both through direct assessment with study staff and by observation through a video camera. Medical staff will evaluate subjects and may make a determination to halt study participation if the subject becomes too behaviorally impaired or if there are emergent safety issues. Subjects who have a BAL greater than 0.04 g/dl or who appear to be too behaviorally impaired to leave our research center will be asked to remain in the clinic until their intoxication is reduced to a level that it is safe to discharge them from the research laboratory. BAL readings will be taken twice to confirm BAL is not greater than 0.04 g/dl prior to release. Subjects will

Pitolisant effects on alcohol self administration and craving in heavy drinkers Version 1.10 7.7.2022 not be released within 60 minutes of their last drink consumed to ensure that peak BAC has been reached prior to discharge. During the descending BAL period, subjects will have access to a comfortable space with entertainment (streaming media), snacks, non-alcoholic beverages, and a nearby bathroom.

#### **Risks of suicidality**

Following consent at screening and during subsequent visits, suicidal ideation and behavior will be assessed using a validated measure (C-SSRS) by trained and credentialed staff including the study PI (PhD, Clinical Psychology), study physician (MD), study nurse (RN, MSN), and project manager (LMHC). All suicidality assessments are completed during in-person visits and are reviewed in real time. Staff who perform suicidality assessments are experienced in managing suicidal ideation and behavior. Clinical staff will work with subjects to ensure a plan for safety, and if this cannot be achieved will escalate to a higher level of care. Subjects will be escorted to the BMC Emergency Department in the case of emergent suicidal ideation. All subjects who have any suicidal ideation will be educated about the Boston Emergency Services Team and will be given the toll-free number for the BEST team.

#### **Risk of loss of confidentiality**

There is some risk that health information collected as part of this study could be seen by unauthorized individuals. Every effort will be made to minimize this risk and protect subject confidentiality. Before a subject agrees to allow study staff to mail study materials to their home address, they will be asked to carefully consider the risk of others learning that they are participating in the study in the event that mail containing study materials is intercepted. Electronic data will be housed in the REDCap data management system. REDCap is protected via Secure Sockets Layer (SSL) encryption that provides access restriction options. Exported data from REDCap will be stored on a secure password-protected server behind the BMC firewall. Source and CRF binders will be stored in a double-locked area that is accessible to only study staff. Subjects will be assigned a study identification number and this will be used to code any forms that do not require the subject's direct identifiers (e.g., consent form, laboratory results, and contact information). A linking key that associates study ID with direct identifiers will be stored in a double-locked cabinet accessible only by study team members. Data will be stored on a password-protected computer accessible only to the study team. Video of subjects during the drinking session will be stored on an encrypted drive with password protection. Video files will be deleted at the end of the study. All study staff will receive appropriate training for the protection of human subjects (NIH Protecting Human Research Participants, CITI Training). A certificate of confidentiality will be sought to protect subjects from disclosure under court order or subpoena.

#### 6.2 Potential Benefits

There is no potential direct benefit to participation in this study. This study presents a very strong potential for benefit to science. Drug development for treating AUD is costly and few pharmaceutical companies are testing novel compounds as agents to treat AUD. Re-purposing

compounds with FDA approval for other indications is the most promising route for rapid and cost-effective development of medications to treat AUD. This study will bridge the gap in drug development by providing a test of pitolisant to see if it may be a candidate drug for treating AUD. If successful, this could lead to the expansion of pharmacotherapy options to treat AUD and a broadening of our understanding of the mechanistic approach to treating AUD.

## 6.3 Analysis of Risks in Relation to Benefits

Given that pitolisant has FDA approval for another indication and is well-tolerated in other populations, the risk to human subjects has been established through pre- and post-marketing data. With the protections we have in place, we believe the risks of this study are well minimized. The study holds significant promise for informing new models of care given the novel mechanism of pitolisant. We believe the risk/benefit ratio is favorable.

## 7 Study Subject Selection

## 7.1 Subject Inclusion Criteria

In order to be eligible to participate in this study, an individual must meet all of the following inclusion criteria:

- 1. 21-55 years of age
- 2. Able to verify age with a state or federal picture ID
- 3. Exceeds safe weekly drinking limits during the 28 days prior to consent (average of 14 drinks for women or 21 drinks for men per week)
- 4. Reports at least one episode of binge drinking (>3 drinks for women, >4 drinks for men) in the 28 days prior consent.
- 5. Meets DSM-5 criteria for mild alcohol use disorder or greater severity.

#### 7.2 Subject Exclusion Criteria

An individual who meets any of the following criteria will be excluded from participation in this study:

- 1. Does not have a smartphone to complete medication exposure period study assessments
- 2. Seeking treatment for alcohol problems
- 3. Clinical Institute Withdrawal Assessment at  $\geq 10$
- 4. DSM-5 diagnosis of current major depression, bipolar disorder, schizophrenia, bulimia/anorexia, insomnia disorder or a substance use disorder other than alcohol, nicotine, marijuana or caffeine
- 5. If female, pregnant, nursing, have plans to become pregnant
- 6. If female, does not agree to use an accepted form of birth control
- 7. Has a medical contraindication to the use of pitolisant
- 8. Has diagnosed medical or mental condition for which further alcohol exposure at the planned dose range would be contraindicated
- 9. Current risk of suicidality (MINI suicidality score greater than 8 (low risk) or Yes to the ideation question #4 of the C-SSRS)

- 10. BMI is greater than 40 or less than 18
- 11. Impaired renal function (GFR <80 mL/min)
- 12. Has a history of any clinically significant renal or hepatic disease
- 13. Child-Pugh Score equal to or greater than Class B (evaluated based on presence or absence of encephalopathy and ascites, INR, bilirubin, and albumin) [https://www.mdcalc.com/child-pugh-score-cirrhosis-mortality]
- 14. Has a clinically significant ECG as determined by the investigator or abnormal ECG heart rate (<45 or >100 bpm) or QTc interval corrected for heart rate using the Fridericia formula (QTcF) > 450 msec
- 15. Has a history of cardiac arrhythmias or who for other reasons are at risk for developing Torsade de Pointes including those with bradycardia, hypokalemia, and congenital QT interval prolongation
- 16. Has a history of dementia
- 17. Has received alcohol counseling or other non-pharmacologic intervention to treat AUD in the past 90 days
- 18. Has taken medications that are used to treat AUD in the past 90 days
- 19. Is currently taking medication that is a sensitive CYP3A4 substrate
- 20. Is currently taking a QTc prolongation agent
- 21. Has urine toxicology results positive for cocaine, opioids, amphetamines, buprenorphine, methadone, methamphetamines, oxycontin, barbiturates, or benzodiazepines.
- 22. Subject is taking a medication which will significantly alter drug metabolism (e.g., strong CYP2D6 inhibitors, strong CYP3A4 inducers, or H1 receptor antagonists that cross the blood barrier (e.g. diphenhydramine or meclizine).
- 23. Subject has known hypersensitivity to pitolisant and any of its components, riboflavin, and/or lactose.
- 24. Subject is known to be a poor CYP2D6 metabolizer.
- 25. Subject is unable to comfortably abstain from nicotine for a period of 8 hours.
- 26. Has COPD, history of solid organ transplant, sickle cell disease, severe heart disease or other health condition for which exposure to COVID-19 represents an unreasonable risk as determined by the study staff physician using accepted COVID-19 guidance (e.g. Centers for Disease Control, etc.).

## 8 Study Intervention

## Study Medication

Study medication will be packaged by the BMC Investigational Pharmacy Service. Pitolisant 4.45 mg pills will be over-encapsulated with 25 mg of riboflavin and pitolisant 17.8 mg pills will be over-encapsulated with 50 mg of riboflavin which will serve as a tracer of medication compliance using urine obtained on the day of the alcohol challenge. Matching placebo will also be packaged using lactose and 25 mg (4.45 mg pill) or 50 mg (17.8 mg pill) of riboflavin. Medication will be dispensed to each subject in two bottles. One bottle will contain 14 pills of pitolisant (4.45 mg) or placebo and the other bottle will contain 5 pills of pitolisant (17.8 mg) or placebo. Capsule size required will be determined by IPS with the goal of a minimum capsule size needed for over-encapsulation. If a subject reports losing (or destroying) study medication, a replacement prescription will be written by one of the study physicians and the BMC Investigational Pharmacy will dispense additional medication to replace the lost (or destroyed) medicine.

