defined as  $\geq$  35 standard drinks per week for men, and  $\geq$  28 standard drinks per week for women. This stratified randomization will minimize the possibility that the order of study drug administration seems to influence outcomes when order effects are actually related to differences in severity of drinking between the two groups of subjects who are receiving the study medication in a different order. On the day of randomization, subjects will undergo an alcohol breath test, urine drug screening, urine pregnancy testing, assessment of concomitant medications, and the TLFB to ensure eligibility. Subjects who have purposefully abstained from drinking and achieved 14 days of abstinence prior to the challenge will be discontinued from participation for ethical reasons. Eligible subjects will be randomized and will receive a 12-day supply of over-encapsulated pitolisant or a matched placebo. Subjects will be scheduled for an alcohol challenge trial within 19 days of randomization. Subjects will be contacted to remind them to start taking study medication twelve days prior to the scheduled alcohol challenge trial. Subjects will be allowed to delay start of medication for up to 7 days after randomization in order to accommodate scheduling for the alcohol challenge trial.

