#### Drug exposure period:

Randomized subjects will receive 12 days of study medication at the time of randomization. A riboflavin tracer (25 mg for 4.45 mg pill; 50 mg for 17.8 mg pill) will be added to each capsule to serve as an objective measure of medication adherence using urine obtained on the day of the alcohol challenge. Two bottles will be dispensed to each subject. One bottle will contain 14 pills of pitolisant (4.45 mg) or placebo and the other bottle will contain 5 pills of pitolisant (17.8 mg) or placebo. All pills will be over-encapsulated with 25 mg (4.45 mg pill) or 50 mg (17.8 mg pill) of riboflavin. Subjects will take an 8.9 mg dose (two 4.45 mg pills) of pitolisant or placebo

once per day on day 1 through 7. Subjects will then take a 17.8 mg dose (one 17.8 mg pill) of pitolisant or placebo once per day on day 8 through 12. The 17.8 mg pill will be overencapsulated with 50 mg of riboflavin. Based on the published half-life for pitolisant, subjects should reach steady state levels after 5 days of taking the 17.8 mg dose. This dosing plan is consistent with the FDA approved prescribing information for the treatment of narcolepsy.

During the twelve-day period of drug exposure, subjects will be asked to answer a medication compliance question each day by smartphone using the REDCap data capture App. In addition to assessing medication compliance, subjects will also be asked to rate their craving for alcohol each day using the alcohol VAS. Subjects will receive a \$5 reimbursement on each day they complete the VAS and answer the medication compliance question using the REDcap smartphone App. Sleep quality during the drug exposure period will also be assessed by having subjects complete items from the National Sleep Foundation Sleep Diary each day. Items to be completed will include daily reports on the total number of hours slept per night and on the number of times and number of minutes for awakening during the night.

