### Medication Visit #2

After the 7-14 day washout period subjects will return to the lab to receive study medication prior to the alcohol challenge #2. Subjects will complete the same tests and interviews completed during the randomization visit (See appendix A for schedule of events). Based on the assessments at medication visit #2, subjects be discontinued for the following reasons: pregnancy, recreational drug use except for marijuana, evidence of non-compliance with study medication, suicidal thoughts or behavior, and use of a new medication that would make participation unsafe. Subjects will receive a 12-day supply of study medication and will be scheduled for the alcohol challenge #2. Subjects will be allowed to delay start of medication for up to 7 days after randomization in order to accommodate scheduling for the alcohol challenge trial.

Alcohol Challenge Trials 1 & 2: Subjects will return to the laboratory on day 12 of drug exposure for each medication trial to complete the alcohol challenge. For safety reasons, subjects will be asked to arrange transportation plans (no driving) prior each of the alcohol challenge trials. There will be a 7-14 day washout period between alcohol challenge Trial 1 and medication visit #2. The washout may extend to 14 days to accommodate the scheduling of the medication visit. Concomitant medications, urine drug screening, urine pregnancy testing, blood alcohol level will be assessed to determine eligibility to proceed with the challenge. Blood alcohol level must be 0.000 to continue with the study procedures. Urine collected for drug screening will be exposed to ultraviolet light as an objective test of medication compliance. If no fluorescence is observed in the urine sample the subject will be excluded from continuing with the challenge. Measures of drinking (TLFB) and cravings (OCDS, VAS and AUQ) will be collected to inform secondary outcomes. Subjects will be observed taking the morning dose of pitolisant (or placebo) on the day of the challenge (after compliance is confirmed via a urine screening). The peak plasma concentration of pitolisant should be reached approximately 60 minutes after administration. The alcohol self-administration session will begin no sooner than one hour after the administration of the observed 17.8 mg morning dose. The alcohol selfadministration will be conducted in the GCRU. The room will be a carpeted and furnished with

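### The challenge-day urine fluorescence check has no capsule-free reference and no control of other riboflavin sources, so a subject who skipped capsules at home can pass it

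*Combined protocol and SAP*

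**What the plan says.** Section 8 (Study Medication) puts 25 mg of riboflavin with each 4.45 mg pill and 50 mg with each 17.8 mg pill, "which will serve as a tracer of medication compliance using urine obtained on the day of the alcohol challenge". Placebo carries the same tracer: "Matching placebo will also be packaged using lactose and 25 mg (4.45 mg pill) or 50 mg (17.8 mg pill) of riboflavin".

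Section 9 (Alcohol Challenge Trials 1 & 2) describes the reading: "Urine collected for drug screening will be exposed to ultraviolet light as an objective test of medication compliance". The rule attached to it is: "If no fluorescence is observed in the urine sample the subject will be excluded from continuing with the challenge". No cut-off or reference sample is stated. The day-12 dose is then taken under observation, after the urine check and at least one hour before the drinking session begins.

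Riboflavin appears in the eligibility criteria only in exclusion 23: "Subject has known hypersensitivity to pitolisant and any of its components, riboflavin, and/or lactose". Concomitant medications are recorded at every visit, but nothing asks specifically about vitamins or supplements, and nothing links them to how the urine is read.

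Urine is also collected when the subject should be off capsules. Section 9 says "On the day of randomization, subjects will undergo an alcohol breath test, urine drug screening, urine pregnancy testing", and of medication visit #2 it says "Subjects will complete the same tests and interviews completed during the randomization visit". Appendix A marks a urine drug screen at both visits. No UV reading is planned at either.

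Other adherence information comes from the daily phone question ("subjects will be asked to answer a medication compliance question each day by smartphone using the REDCap data capture App"), from capsule counts (Section 8, Medication accountability), and from a provision to discontinue a subject at medication visit #2 for evidence of non-compliance. That evidence is not defined.

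**The concern.** The tracer and riboflavin from any other source are the same substance. If a subject's urine fluoresces without capsules, the check reports compliance whether or not capsules were taken. The plan has no means of finding out which subjects these are. The placebo period cannot show it, because placebo capsules also contain riboflavin. The only periods meant to be free of capsules are before randomization and the washout, and urine from those times is not read.

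Fluorescence is the only adherence condition that the plan states for entering a challenge on the day. A subject who passes wrongly in the pitolisant period enters the primary analyses of consumption and craving without the exposure the design intends. Section 9 (Drug exposure period) expects steady state after five days at 17.8 mg, and this subject would not have had those days. The comparison could then be pulled toward no effect. After a null result, fluorescence could not separate an ineffective drug from a drug not taken in subjects with another riboflavin source.

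**Working it through.** **Inputs from Section 12.2:** 28 completers; effect size d = 0.7; reduction of 1.5 standard drinks; SD of within-subject differences 2.1; alpha 0.01; power 0.81. The plan does not say whether alpha is one- or two-sided.

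**Plan's own figure.** For a paired t-test, the noncentrality is d × √n = 0.70 × √28 = 3.704, with 27 degrees of freedom and a two-sided 1% critical value of 2.771. Power is 0.815, and 28 is the smallest n that reaches 0.81. The stated figure reproduces with a two-sided test. One-sided would give 0.883.

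**Inputs the documents do not give (assumptions):**
- q, the share of completers who pass the check in the pitolisant period after skipping capsules at home. If 20-30% of subjects take riboflavin supplements and 10-20% of those skip capsules, then q runs from 0.20 × 0.10 = 2% to 0.30 × 0.20 = 6%. This also assumes that every supplement user's urine fluoresces visibly and that supplement use is unrelated to adherence.
- e, the share of the full effect that such a subject keeps through the single observed dose. Two values are shown: 0.5 and 0. The second is the worst case.

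**Formula.** Diluted effect size = 0.70 × (1 − q × (1 − e)), with the SD held at 2.1. Power comes from the same paired t calculation at n = 28.

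| q | e | Diluted d | Power |
|---|---|---|---|
| 0 | – | 0.700 | 0.815 |
| 2% | 0.5 | 0.70 × 0.99 = 0.693 | 0.806 |
| 6% | 0.5 | 0.70 × 0.97 = 0.679 | 0.786 |
| 2% | 0 | 0.70 × 0.98 = 0.686 | 0.796 |
| 6% | 0 | 0.70 × 0.94 = 0.658 | 0.755 |

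The loss is about 1 to 3 percentage points with half the effect kept and 2 to 6 with none kept. Skipping counts here only in the pitolisant period. A subject who skips placebo capsules does not dilute the effect.

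**The case against.** The strongest reply is the observed dose. A reader might infer that a subject who slips through reaches the challenge with no pitolisant and contributes a difference centred on zero. Section 9 does not support that. In the pitolisant period every subject who goes on to the challenge takes 17.8 mg under observation, and the protocol expects peak plasma concentration about 60 minutes later. The affected subject is under-exposed, not unexposed, and a difference of zero is only a worst case. This part of the reply stands.

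The size is also uncertain. The documents do not say how often, or how strongly, riboflavin from other sources makes urine fluoresce compared with 25-50 mg capsules, and both factors behind q are assumed. With the protocol's unrounded inputs (1.5/2.1 = 0.714), power starts at 0.834. At q = 5% with half the effect kept, d is 0.714 × 0.975 = 0.696 and power is still 0.811. This stands too. It limits what can be said about magnitude, but does not show that the check works.

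The plan also has other layers: the daily app question, capsule counts, accountability at both trial visits, and possible discontinuation at medication visit #2. That last provision means non-compliance in period 1 can keep a subject from Challenge 2, so fluorescence is not the only adherence evidence with consequences. But it comes too late for Trial 1 and before any period-2 dosing, and it has no stated criterion. The app and the counts rest on self-report and returned bottles, and no challenge-entry rule is tied to them. The gap on the challenge day remains.

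**Conclusion.** The point holds as a specific, inexpensive weakness in the adherence check. The stated rule passes any fluorescence, and the plan neither controls other riboflavin sources nor reads capsule-free urine. It therefore cannot detect skipped home doses in a subject whose urine fluoresces anyway.

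The documents do not give the size of the consequence. Under the assumed 2-6% of affected completers, power falls from 0.815 to 0.806-0.786 with half the effect kept, or to 0.796-0.755 with none kept. Those ranges rest on assumed rates, an assumed retained effect, d = 0.70, two-sided alpha 0.01 and an unchanged SD. They do not support a claim that the trial is seriously underpowered, or that the primary comparison includes subjects who took no pitolisant.

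**What to change.** 1. Read the drug-screen urine already collected at the Randomization visit under the same UV lamp, and use it as the subject's capsule-free reference.
2. Ask subjects to avoid riboflavin-containing supplements in both exposure periods. Record any use with the concomitant medications at each visit, including the challenge days. This is needed as well as the reference, because the Randomization sample is taken 12 to 19 days before Challenge 1 and can miss intermittent use.
3. Where the reference sample fluoresces or supplement use is reported, do not take challenge-day fluorescence alone as proof of compliance. Judge it together with the capsule count and the daily app log.
4. Read the Dispense-visit urine too, but treat fluorescence there only as a prompt to ask about supplements or leftover period-1 capsules. The reading cannot tell the two apart.

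The cost is a few lines of protocol text, two extra lamp readings per subject on urine already in hand, and a minor supplement restriction. For a few subjects, compliance will rest on weaker evidence. Visits and sample size are unchanged. The fix does not verify the earlier dosing days: a subject who takes only a recent capsule would still pass.
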